Secondary Endpoint(s)	
 
Change from baseline in the blood (serum) and esophageal TGF-<math>\beta</math> levels in participants receiving losartan potassium at the EOT visit (or at early withdrawal) as determined by research blood samples and EGD with biopsy, respectively.
 
Normalization of the EoE transcriptome in participants receiving losartan at the EOT visit (or at early withdrawal) as determined by EGD with biopsy.
 
Change from baseline in histopathology in participants receiving losartan potassium at the EOT visit (or at early withdrawal) as determined by EGD with biopsy.
 
Change from baseline esophageal compliance in participants receiving losartan at the EOT visit (or at early withdrawal) as determined by EndoFLIP.
 
Change from baseline PFC (Pediatric Eosinophilic Esophagitis Symptom Severity [PEESS], PedsQL Eosinophilic Esophagitis Module [PedsQL™ EoE], EoE Quality of Life Questionnaire, and EEsA) in participants receiving losartan at the EOT visit (or at early withdrawal) as determined by EndoFLIP.
 

Accrual Objective	
 
It is estimated that 30 patients will need to be screened for a total of approximately 15 participants enrolled in the study. Of the 15 participants enrolled, at least one third will have evidence of EoE with CTD, whereas the remaining participants will have no evidence of a CTD.
 

Study Duration	
 
Total duration of treatment is approximately 16 weeks. During the titration phase, participants will be on titrated doses of losartan for 4 weeks. During the maintenance phase, participants will be on a stable dose of treatment for 12 weeks.
 

Treatment Description	
 
• During the study oral administration of losartan tablets or suspension occurs once a day, at about the same time each day, throughout the treatment period. The dose of the study agent to be administered will depend on the participant's body weight and will be calculated (mg/kg) on the basis of a titration schedule during the treatment (i.e., titration and maintenance) phase, not to exceed the daily dose of 100 mg. The medication dosage for losartan potassium will change throughout this study, titrating to a higher dose.
 

------------------------------	---

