### 12.5 Sample Size Considerations

Five patients with EoE-CTD and 10 patients with EoE will be recruited into the study. Since this represents a pilot study to evaluate whether the treatment affects endpoints, the sample size was not selected on the basis of power considerations for statistical testing. The estimates of treatment effect from this study will be used to power future studies. Based on historical data from the [REDACTED], it is estimated that the standard deviation of the change from baseline at 12 weeks based on the square root transformation of the eosinophil/HPF values will be approximately 5. Table 7 provides the width of the two-sided 95% confidence interval for the change from baseline in eosinophil/HPF for various scenarios of sample size and standard deviation.

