This is a phase II, open-label trial of losartan in patients diagnosed with EoE with or without a CTD. Prior to entry, patients must meet the current consensus criteria for EoE in which efforts are made to rule out other causes of esophageal eosinophilia. The trial will perform a preliminary assessment of the effect of the maximum tolerated dose of losartan in participants with active EoE as determined by the absence of side effects and by vital signs being within normal limits. The primary endpoint of the study is the reduction in the number of esophageal eosinophils in participants who will receive losartan orally once a day (Figure 1). The primary safety endpoint is descriptive and will require reporting of SAE or Grade 3 and above AEs.

Figure 1 Study Design Flowchart

Analysis Populations

The analysis population for the primary and secondary endpoints will be participants who received Losartan and maintained the baseline EoE treatment throughout the course of the study.

Statistical Considerations and Analytical Plan

Overview

Change from baseline for eosinophil counts will be calculated for each participant. The average change from baseline within each group and combining both groups (i.e. EoE and EoE-CTD) will be calculated along with the corresponding two-sided, 95% confidence interval. Additionally, we will perform paired tests which will specifically test whether there was significant change between baseline and study completion. The last observation carried forward (LOCF) method will be used for participants who end the trial early. To assess changes over time for continuous secondary and safety outcomes, a mixed effects model for repeated measures analysis will be used. Unless stated otherwise, all statistical testing will be done at $\alpha=0.05$.

Variables of Interest

Primary outcome:

- 1) Change in eosinophils/hpf from baseline to post treatment
- 2) Rate of SAE / Grade 3 or above AE

Secondary outcomes:

- 1) Blood (serum) and esophageal TGF- β levels
- 2) EoE transcriptome
- 3) Histopathology as assessed by the Histology Scoring System (HSS): Will include the overall score, grade score, stage score, and the inflammatory and structural sub-scores. Scores will be reported as distal, proximal, and maximum
- 4) Esophageal compliance as measured by EndoFLIP.
- 5) PROS (Pediatric Eosinophilic Esophagitis Symptom Severity [PEESS], PedsQL Eosinophilic Esophagitis Module [PedsQLTM EoE], EoE Quality of Life Questionnaire, and EEsAI)

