Prior to any hypothesis testing, all variables will be reviewed for plausibility. Any values which are considered suspect will be reviewed by the clinical team to ensure accuracy. Continuous data will be evaluated for distributional assumptions of normality. Natural log-transformation will be considered for right skewed non-normally distributed data (the most typical skew seen in physiologic data).

Demographics/Patients Characteristics

Demographic, patient characteristics, medication use, and study completion status will be summarized using median [interquartile range] for continuous variables and frequency and percentages for categorical variables. Treatment comparisons will be performed for demographics and patient characteristics using the Wilcoxon Rank sum test for continuous variables and the Fisher's Exact test for categorical variables. All tests will be conducted at $\alpha=0.05$.

Analysis of Primary Outcome

Primary Objective:

1. To assess the effect of losartan on the reduction of esophageal eosinophils in participants with EoE with or without a CTD.

Change from baseline for eosinophil counts will be calculated for each participant. The average change from baseline within each group and combining both groups (i.e. EoE and EoE-CTD) will be calculated

along with the corresponding two-sided, 95% confidence intervals. If the assumption of normality is not viable for the change from baseline score, we will use a square root transformation on the eosinophil counts prior to calculating the change from baseline and determine if the “change score” attains normality. If this transformation is not successful, the median of the change will be calculated along with the 95% confidence interval for the median using Hodges-Lehmann estimators. Each confidence interval will be visually inspected to determine if zero is a possible value for the true change from baseline (μ). This corresponds to testing the following hypothesis:

H0: $\mu=0$ vs. H1: $\mu\neq 0$.

The last observation carried forward (LOCF) method will be used for participants who end the trial early.

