Additionally, to evaluate the effect of losartan on the reduction of esophageal eosinophils in participants with EoE (with or without a CTD), we will use paired non-parametric Wilcoxon Rank sum test. The Wilcoxon rank sum paired test will be used given the small sample size and the broad range of eosinophils which could be present in our participants. Analyses will be performed using the whole cohort and stratified by CTD. Statistical significance will be set at $\alpha = 0.05$. This corresponds to testing the following hypothesis:

H0: baseline and study completion are equal vs. H1: baseline and study completion are not equal.

Analyses of Secondary Endpoint(s)/Outcome(s)

To assess changes over time for continuous secondary and safety outcomes, a mixed effects model for repeated measures analysis will be used. The dependent variable will be the change from baseline. The “participant nested within group” term will be considered a random effect. Time (i.e. measurement time) will be included as a continuous effect. Terms in the model will be time, group (i.e., EoE and EoE-CTD), and time-by-group interaction. The baseline value will be used as a covariate in the model. If necessary, to meet the assumptions of the analysis, an appropriate transformation will be used (e.g., square root, log, rank). The hypotheses that will be tested are whether there is a significant trend over time and whether this trend is consistent between the CTD and non-CTD groups (i.e. testing the interaction term). If the trend is not consistent between groups based on the statistical test at $\alpha=0.10$, we will estimate the trend within each of the two groups by including terms in the statistical model that estimates the trend within each group and the hypothesis to be tested within each group is whether this trend is significantly different than zero. We will systematically assess the residuals to determine whether a linear or quadratic model best fits the data. In statistical terms, the hypotheses are provided below.

For testing consistency of the time trend (β) between the CTD and non-CTD group, the hypotheses are:

H0: $\beta_{\text{EoE-CTD}} = \beta_{\text{EoE (non-CTD)}}$ vs. H1: $\beta_{\text{EoE-CTD}} \neq \beta_{\text{EoE (non-CTD)}}$.

For testing linear trend combining across groups (if there is consistency of the time trend):

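### With the planned five EoE-CTD participants, the added paired Wilcoxon test cannot reach p<0.05 if done exactly (minimum 0.0625), and the SAP misnames it a rank sum test

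*SAP*

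**What the plan says.** The SAP, Analysis of Primary Outcome, starts with the mean change from baseline in eosinophil count and its 95% confidence interval, within each group and combined. If normality fails it moves to square-root counts. If that fails too, it gives the median change with a "95% confidence interval for the median using Hodges-Lehmann estimators". It then adds a test: "we will use paired non-parametric Wilcoxon Rank sum test". The stated reasons are the small sample and the wide range of counts. Alpha is 0.05, the alternative is two-sided, and "Analyses will be performed using the whole cohort and stratified by CTD". It does not say whether the p-value is exact or asymptotic.

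On the size of the CTD stratum, Protocol 12.5 states: "Five patients with EoE-CTD and 10 patients with EoE will be recruited into the study". The synopsis is looser: "at least one third will have evidence of EoE with CTD".

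Two further rules affect how many usable pairs there will be. The SAP limits the analysis population to "participants who received Losartan and maintained the baseline EoE treatment throughout the course of the study". It also states: "The last observation carried forward (LOCF) method will be used for participants who end the trial early".

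Under Demographics/Patients Characteristics the SAP compares groups "using the Wilcoxon Rank sum test for continuous variables". There the name is correct, because that comparison is unpaired.

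**The concern.** A signed-rank test on five pairs has so few possible outcomes that its smallest exact p-value may lie above the declared alpha. The test would then be pre-specified in the CTD stratum with no possible result that meets its own criterion. That differs from low power: no effect, however large or consistent, would change it.

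Two consequences follow. First, a non-significant CTD result beside a significant result in the ten EoE participants could be read as a difference between subgroups when it only reflects the number of pairs. Second, if some approximations fall below 0.05 and the exact test does not, the result depends on a choice that the SAP leaves open and that could be made after the data are seen.

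The name adds ambiguity, because the SAP uses one label for a paired and an unpaired procedure.

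**Working it through.** **Inputs.** Planned EoE-CTD n = 5, EoE n = 10, total 15 (Protocol 12.5). Alpha 0.05, two-sided (SAP, Analysis of Primary Outcome). SD of change 5 on the square-root scale (Protocol 12.5).

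**1. The plan's own figure at n=5.** The documents give no p-value or power for the Wilcoxon test. The nearest figure is the Table 7 half-width. With t(0.975, n-1) × SD/√n, n=5 and SD 5 give 2.776 × 5/2.236 = 6.21 (printed ±6.2), and SD 10 gives 12.42 (printed ±12.4). Table 7 is therefore t-based. That interval has no floor and can exclude zero at n=5.

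**2. Exact minimum p.** Under the null each of the 2^n sign patterns is equally likely, and the most extreme two-sided result has two of them, so minimum p = 2/2^n.

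| Non-zero pairs | Minimum exact two-sided p |
|---|---|
| 4 | 2/16 = 0.125 |
| 5 | 2/32 = 0.0625 |
| 6 | 2/64 = 0.031 |
| 10 | 2/1024 = 0.002 |
| 15 | 2/32768 = 0.00006 |

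Six is the first number that can reach 0.05.

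**3. Approximations at n=5, all changes in one direction, no ties.** The null variance is 5 × 6 × 11/24 = 13.75 (SD 3.708), and the largest departure from the null mean is 7.5.
- Normal, uncorrected: z = 7.5/3.708 = 2.02, p = 0.043.
- Normal, continuity-corrected: z = 7.0/3.708 = 1.89, p = 0.059.
- t approximation to the signed-rank statistic: t = 7.5 × √(4/(5 × 13.75 − 7.5²)) = 4.24 on 4 df, p = 0.013.

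The next most extreme outcome (departure 6.5) gives z = 1.75 and t = 2.53. Neither rejects, against 1.96 and 2.776. The uncorrected normal and the t versions therefore reject only at the two extreme patterns, and their true size is 2/32 = 0.0625, above the declared 0.05. At n=6 the uncorrected normal version has true size 4/64 = 0.0625, against 0.031 for the exact test.

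**4. Hodges-Lehmann fallback.** The widest signed-rank interval has coverage 1 − 2/2^n: 93.75% at n=5 and 96.9% at n=6. No such interval attains 95% with five pairs.

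**5. Usable pairs can be fewer than participants.** Under LOCF, a participant with no end-of-treatment or withdrawal biopsy carries the baseline count forward. The change is then zero, and the standard signed-rank test drops it. Six CTD participants with one such zero have five non-zero pairs, and the minimum returns to 0.0625.

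**6. Power, for scale.** SD of change 5; the mean falls on the square-root scale are my assumption, because the documents give none.

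| Analysis | Fall of 4 | Fall of 6 | Fall of 8 |
|---|---|---|---|
| Exact signed-rank, n=5 | 0% | 0% | 0% |
| Exact signed-rank, n=6 | 24% | 48% | 71% |
| t interval, n=5 | 28% | 53% | 76% |

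Signed-rank power is from 100,000 simulated normal samples, t power from the noncentral t distribution.

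**7. The name taken literally.** An unpaired rank sum test of five baseline against five final counts has minimum p = 2/C(10,5) = 2/252 = 0.008, but it would ignore the pairing.

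**The case against.** The strongest reply is that little depends on this test. The SAP introduces it as an addition to the interval analysis, no decision in the documents turns on the stratum p-value, and both documents describe the study as preliminary and descriptive. Protocol 12.5 says the sample was not sized for hypothesis testing, and Table 7 openly shows how imprecise n=5 is. This stands, and it limits the severity. It also argues for describing the stratum rather than setting a 0.05 threshold in it.

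Five is also not a fixed ceiling. The synopsis gives a minimum of one third, and Protocol 10.3 replaces dosed participants who do not reach Week 16. A withdrawn participant with a biopsy plus a replacement could make six pairs. Early withdrawers are meant to have the end-of-treatment endoscopy and biopsy (Protocol 8.8, 10.4 and Table 4), so a carried-forward zero needs both a withdrawal and a missed biopsy. These points make erosion below five less likely. They do not remove the limit for five completers, which is what the protocol plans.

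The power figures rest on assumed effects that may be optimistic. Counts cannot fall below zero, so a mean fall of 6 needs a mean root baseline of at least 6 (36 eosinophils/HPF) with complete clearance, and 8 needs 64/HPF. Entry requires only 15/HPF, a root of 3.9. The n=6 and t-interval rows are therefore illustrative. The zeros at n=5 hold at any effect size.

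The Hodges-Lehmann point arises only if normality is rejected on both scales. On the name, the word paired shows that the signed-rank test is meant, so an unpaired analysis is unlikely. Both are small corrections.

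**Conclusion.** The concern holds. At five non-zero pairs the stratum test as specified either cannot reject (exact minimum 0.0625, or 0.059 with continuity correction) or rejects only by exceeding its declared alpha (0.043 uncorrected normal or 0.013 t approximation, true size 0.0625). A Hodges-Lehmann interval labelled 95% there would be mislabelled, since its maximum coverage is 93.75%. The rank sum label is wrong for a paired test.

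This assumes the planned five in the CTD stratum, a two-sided test, and the signed-rank test as the intended method. It does not apply with six or more non-zero pairs, to the EoE group, or to the whole cohort. The first-line t interval in the CTD stratum remains able to exclude zero, so CTD inference as a whole is not decided in advance. The point should be fixed, but it affects one supplementary test and not the study's main estimate.

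**What to change.** In the SAP, Analysis of Primary Outcome:
- Name the test as the exact Wilcoxon signed-rank test on within-participant differences, and state how zero differences and ties are handled.
- State that in any stratum with fewer than six non-zero pairs no significance claim at 0.05 is made from the Wilcoxon test. Report the individual changes there, with the interval from the existing sequence (raw scale, then square root, then Hodges-Lehmann).
- Label any Hodges-Lehmann interval from five pairs with its attained level of 93.75%.

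Keep the rank sum name for the unpaired comparisons of patient characteristics. The cost is SAP wording only. Data collection, sample size and the order of the interval methods do not change.

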H0: $\beta=0$ vs. H1: $\beta\neq 0$ where β is the slope of the line across groups. Similar hypotheses will be tested if analysis of the residuals indicates that higher order terms need to be included in the model (e.g. quadratic). If there is strong evidence that the time trend is not consistent between the two groups, we will test the above hypothesis within each of the two groups. In addition, the two-sided, 95% confidence interval for the slopes will be calculated to provide estimates of the slope for future studies.

The percentage of participants for whom peak eosinophil counts are < 15 eosinophil/HPF at Week 16 will be estimated within each CTD group along with a 95% confidence interval.

Safety endpoints that are categorical will be summarized within each group. Further, any SAEs or Grade 3 or above will be reported descriptively.

Software Used (with References) and Specialized Macros (with References)

SAS version 9.4, JMP 14.

This SAP has been reviewed and approved by:

Investigator

Date

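### For PROs, labs and vitals, the trend model has a random participant intercept but no random slope, so slope tests and intervals can be too optimistic if participants' trends differ.

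*SAP*

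**What the plan says.** The SAP, under Analyses of Secondary Endpoint(s)/Outcome(s), and Protocol 12.4 carry the same model.

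- **Scope:** "To assess changes over time for continuous secondary and safety outcomes, a mixed effects model for repeated measures analysis will be used".
- **Fixed part:** "Terms in the model will be time, group (i.e., EoE and EoE-CTD), and time-by-group interaction", with the baseline value as a covariate and change from baseline as the response.
- **Random part:** participant within group is the only factor named. That "term will be considered a random effect. Time (i.e. measurement time) will be included as a continuous effect".
- **Tests:** the model is to show "whether there is a significant trend over time and whether this trend is consistent between the CTD and non-CTD groups". The slope is tested at 0.05 under the SAP's general rule ("Unless stated otherwise, all statistical testing will be done at" 0.05). The interaction is tested at 0.10 and decides whether slopes are reported by group ("If the trend is not consistent between groups based on the statistical test at" 0.10).
- **Use:** "the two-sided, 95% confidence interval for the slopes will be calculated to provide estimates of the slope for future studies".

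Neither document gives a participant-by-time term, a residual covariance structure, robust standard errors or a degrees-of-freedom method. The one planned residual check concerns whether the mean trend is linear or quadratic.

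**The concern.** A random intercept lets participants differ in level but not in slope. The common slope is then judged against visit-to-visit scatter pooled over all participants, with about 44 degrees of freedom for 15 people and four visits. The independent units, however, are the 15 people.

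The protocol gives reasons to expect trends to differ. Ages run from 5 to 25, background diet, swallowed steroid and PPI vary between participants, and dose depends on tolerance. The SAP also plans to classify participants by adherence.

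Two outputs are at stake. The slope intervals are intended for planning later studies, so their width matters more than any p-value. The interaction test selects which analysis is reported, including a separate slope from five EoE-CTD participants.

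**Working it through.** **Inputs from the documents**
- n = 15: 10 EoE and 5 EoE-CTD (Protocol 12.5).
- Labs and vitals after baseline at Weeks 4, 8, 12 and 16, so m = 4. PROs at the same weeks plus Week 20, so m = 5 (Protocol Table 4 and 8.4 to 8.9).
- Nominal levels: 0.05 for the slope, 0.10 for the interaction.

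**Assumption.** k is the SD of true 12-week slopes divided by the residual SD. The documents give neither SD, so k is varied from 0 to 2.

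**Step 1: spread of visit times, in 12-week units**
- m = 4: centred times are ±1/2 and ±1/6, so S = 2(1/4 + 1/36) = 0.556.
- m = 5: centred times are 0, ±1/3 and ±2/3, so S = 2(1/9 + 4/9) = 1.111.

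**Step 2: true against reported standard error.** In balanced data the random-intercept slope is the mean of the participants' own least-squares slopes. Let ρ = k²S, the slope variance divided by the sampling variance of one participant's own slope.
- True variance of the mean slope: (σ²/S)(1 + ρ)/n.
- Variance the model reports, on average: (σ²/S)[1 + ρ(n−1)/(n(m−1)−1)]/n, because part of the slope spread enters the residual.
- Ratio, true to reported SE: √{(1 + ρ)/[1 + ρ(n−1)/(n(m−1)−1)]}.

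The factor (n−1)/(n(m−1)−1) is 14/44 = 0.318 for m = 4 and 14/59 = 0.237 for m = 5.
- m = 4, k = 1: ρ = 0.556; √(1.556/1.177) = 1.15.
- m = 4, k = 2: ρ = 2.222; √(3.222/1.707) = 1.37.
- m = 5, k = 1: ρ = 1.111; √(2.111/1.264) = 1.29.
- m = 5, k = 2: ρ = 4.444; √(5.444/2.055) = 1.63.

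For large ρ the ratio levels off near √(m−1), about 1.7 or 2, so the understatement is bounded.

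**Step 3: rejection rates with no true trend** (simulation, 10 + 5 participants, 40,000 replicates per setting). The row k = 0 reproduces the plan's nominal levels.

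| k | Trend at 5%, m = 4 | Interaction at 10%, m = 4 | Trend at 5%, m = 5 | Interaction at 10%, m = 5 |
|---|---|---|---|---|
| 0 | 5% | 10% | 5% | 10% |
| 0.5 | 6% | 12% | 7% | 13% |
| 1 | 9% | 15% | 13% | 20% |
| 1.5 | 12% | 20% | 19% | 27% |
| 2 | 15% | 23% | 23% | 32% |

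Coverage of the 95% slope interval is 100% minus the trend column, so at k = 2 it is 85% (m = 4) or 77% (m = 5).

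**Step 4: two checks**
- A t-test on the participants' own slopes stays at about 5% (interaction about 10%) throughout.
- Serial correlation alone, which the stated model also leaves out, has a similar effect. With equal slopes and AR(1) correlation of 0.5 between visits, the trend test rejects 11.6% (m = 4) or 13.5% (m = 5).

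**The case against.** **The size is unknown.** A reader might infer that the tests are certainly and badly inflated. The documents do not support that, because they give no slope SD, residual SD or slope SE. With four visits the trend test rejects only 5.2%, 5.9% and 6.9% at k = 0.25, 0.5 and 0.75. With five visits the figures are 5.5%, 7.3% and 9.9%. Small ratios cannot be ruled out for noisy questionnaires or stable labs. This stands, and the point is therefore conditional.

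**The text may be silent rather than wrong.** A repeated-measures mixed model can carry a residual covariance structure, and none is expressly excluded. This stands in part. Still, the plan names its random term and its fixed terms, and an analyst following it would fit a random intercept with independent residuals.

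**Scope.** A reader might take the wording on secondary outcomes to cover all of them. TGF-β, transcriptome, histopathology and EndoFLIP have one post-baseline value, so no within-participant slope can be estimated from the change scores and this problem does not arise.

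**Consequence.** A reader might infer that the trial's main result is compromised. It is not. The primary analysis uses one change per participant, the study calls itself preliminary and descriptive, and with balanced data the slope estimate itself does not move.

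**The fifth visit is off treatment.** Week 20 falls about 30 days after the last dose, so one straight line through it is questionable on other grounds. The four-visit figures are the safer guide.

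**Conclusion.** The point holds, conditionally. For PROs, clinical labs and vitals, the model as written gives nominal error only if participants within a group share one slope and residuals are independent. Otherwise its tests are anti-conservative and its slope intervals too narrow. For k from 0 to 2, the true SE is 1.00 to 1.37 times the reported one with four visits, and 1.00 to 1.63 times with five.

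These figures assume complete balanced data, 15 participants, normal errors and the stated range of k. It would be too strong to say that the model ignores slope differences altogether, since part of them enters the residual and bounds the error. This is a should-fix: the harm is over-narrow intervals carried into later planning, and an interaction test that splits the groups too readily.

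**What to change.** In the SAP, and in Protocol 12.4 or as a documented SAP departure from it, for the repeatedly measured outcomes:

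1. Add a participant-level random slope for time, with Kenward-Roger degrees of freedom.
2. If that model does not converge with 15 participants, fit each participant's own slope. Use a one-sample t analysis for the overall trend (14 degrees of freedom) and a two-sample one for the group comparison (13). If baseline adjustment is wanted, regress the slopes on group and baseline.
3. Take the reported slope intervals from whichever of these analyses is used.
4. List the outcomes covered. State that those with a single post-baseline value are outside this model.

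No new data or visits are needed. The cost is wider slope intervals: about 5–6% wider if slopes are in fact equal, with a small loss of power, and about 30–35% wider at ρ = 1. The fallback gives short and full follow-up equal weight, and a quadratic trend would need the same participant-level treatment. The SAP should say how each is handled.
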